3.8. Analysis Visit Windows

3.8.1. Definition of Study Day

Study day will be calculated from the first dosing date of study drug and derived as follows:

- For postdose study days: Assessment Date – First Dosing Date + 1
- For days prior to the first dose: Assessment Date – First Dosing Date

Therefore, **Study Day 1** is the day of first dose of study drug administration.

First Dosing Date is defined as the minimum, nonmissing, nonzero dose date of treatment recorded on the Study Drug Administration eCRF.

Last Dose Date is defined as the maximum, nonmissing, nonzero dose date of treatment recorded on the Study Drug Administration eCRF with “Check box if study drug was permanently withdrawn” checked for participants who prematurely discontinued or completed study drug according to the Study Drug Completion eCRF.

Last Study Date is the latest of the study drug start dates and end dates, the in-person or virtual visit dates, the vital sign collection dates, the questionnaire collection dates, the laboratory collection dates, and the death date (if applicable, for participants who died during the study, the death date will be the Last Study Date. For participants who died after completing the study or after prematurely discontinuing the study, the death date will not be considered for the Last Study Date).

Baseline value is defined as the last value obtained on or prior to the first dose date (and time, if available), unless otherwise specified.

3.8.2. Analysis Visit Windows

Participant visits might not occur on protocol-specified days. Therefore, for the purpose of analysis, observations will be assigned to analysis windows.

The analysis windows for body weight and height/length/head circumference are provided in Table 3-1.

Table 3-1. Analysis Visit Windows for Body Weight and Height/Length/Head Circumference

Visit	Study Day	Visit Window Study Day	
		Lower Limit	Upper Limit
Baseline	1	(none)	1
Day 10	10	2	≥ 10

The analysis windows for vital signs and RSV nasal swab viral load are provided in Table 3-2.

Table 3-2. Analysis Visit Windows for Vital Signs and Nasal Midturbinate Swab Samples

Visit	Study Day	Visit Window Study Day	
		Lower Limit	Upper Limit
Baseline	1	(none)	1
Day 3	3	2	4*
Day 5	5	4*	7
Day 10	10	8	≥ 10

* If the nominal visit is a scheduled visit and the assessment is done on Day 4 (Study Day = 4), assign to Day 3 or Day 5 analysis window based on the nominal visit label. If the nominal visit is an unscheduled visit or early discontinuation visit on Day 4, assign to Day 3 analysis window.

The analysis windows for clinical laboratory assessments are provided in Table 3-3.

Table 3-3. Analysis Visit Windows for Hematology and Chemistry Laboratory Assessments

Visit	Study Day	Visit Window Study Day	
		Lower Limit	Upper Limit
Baseline	1	(none)	1
Day 5	5	2	8*
Day 10	10	8*	≥ 10

* If the nominal visit is a scheduled visit and the assessment is done on Day 8 (Study Day = 8), assign to Day 5 or Day 10 analysis window based on the nominal visit label. If the nominal visit is an unscheduled visit or early discontinuation visit on Day 8, assign to Day 5 analysis window.

CCI

The analysis windows for palatability and acceptability are provided in Table 3-4.

Table 3-4. Analysis Visit Windows for Palatability and Acceptability Assessments

Visit	Study Day	Visit Window Study Day	
		Lower Limit	Upper Limit
Baseline	1	(none)	1
Day 5	5	2	≥5

3.8.3. Selection of Data in the Event of Multiple Records in an Analysis Visit Window

Depending on the statistical analysis method, single values may be required for each analysis window. For example, change from baseline by visit usually requires a single value, whereas a time-to-event analysis would not require 1 value per analysis window.

If multiple valid, nonmissing measurements exist in an analysis window, records will be chosen based on the following rules if a single value is needed:

- For baseline questionnaire data, the last nonmissing value on or prior to the first dosing date of study drug will be selected. If there are multiple records on or prior to the first dosing date, the record prior to and closest to the first dosing date and time will be used if available; otherwise, the record after and closest to the first dose date and time will be used.
- For baseline data other than questionnaire, the last nonmissing value on or prior to the first dosing date of study drug will be selected, unless specified differently. If there are multiple records on the same day, the baseline value will be selected as follows:

— For continuous data:

- For RSV viral load and infectious viral titer data, if there is more than 1 record on the selected day, the latest value will be selected. Within each of viral load sample category types, if there are multiple records with the same time or no time recorded on the same day, the geometric mean value will be taken.
- For other continuous data, the baseline value will be the average of the measurements.

- For categorical data:
 - For RSV positivity based on RT-qPCR, Multiplex PCR, the worst severity (ie, a positive PCR result) will be selected.
 - For other categorical data, the baseline value will be the measurement with the lowest severity.
- For postbaseline values:
 - The record closest to the nominal day for that visit will be selected.
 - If there are 2 records that are equidistant from the nominal day, the later record will be selected.
 - If there is more than 1 record on the selected day, values will be selected for analysis as follows:
 - For RSV viral load and infectious viral titer, if there is more than 1 record on the selected day, the latest value will be selected. If there are multiple records with the same time or no time recorded on the same day, the geometric mean value will be taken.
 - For questionnaire data to be summarized, if there is more than 1 record on the selected day, the latest value will be selected.
 - For other parameters, if there is more than 1 record on the selected day, the average will be taken for continuous data and the worse severity will be taken for categorical data, unless otherwise specified.

4. PARTICIPANT DISPOSITION

4.1. Participant Enrollment and Disposition

Key study dates (ie, first participant screened, first participant randomized, last participant randomized, and last participant last visit for the clinical study report) will be provided.

A summary of participant enrollment will be provided by treatment group (overall and within each cohort/weight group) for each investigator within a country, and overall using the All Randomized Analysis Set. The summary will present the number and percentage of participants enrolled. For each column, the denominator for the percentage calculation will be the total number of participants analyzed for that column.

A summary of participant disposition will be provided by treatment group (overall and within each cohort/weight group) and overall. This summary will present the number of participants screened, the number of participants who met all eligibility criteria but were not randomized with reasons for participants not randomized, the number of participants randomized, and the number of participants in each of the categories listed below:

- Safety Analysis Set
- Full Analysis Set
- Full Analysis Positive Set
- PK Analysis Set
- Virology Analysis Set
- Completed study drug
- Did not complete study drug with reasons for premature discontinuation of study drug
- Completed study
- Did not complete the study with reasons for premature discontinuation of study

For the status of study drug and study completion and reasons for premature discontinuation, the number and percentage of participants in each category will be provided. The denominator for the percentage calculation will be the total number of participants in the Safety Analysis Set corresponding to that column.

The following by-participant listings will be provided by participant ID number in ascending order to support the above summary tables:

- Participant disposition, including cohort/weight group, treatment group, date of randomization, first dose date, last dose date, end of study date, study drug discontinuation, study discontinuation, and reasons for study drug or study discontinuation.
- Reasons for screen failure (will be provided by screening ID number in ascending order)

4.2. Extent of Study Drug Exposure and Adherence

Extent of exposure to study drug will be examined by assessing the total duration of exposure to study drug and the level of adherence relative to the study drug regimen specified in the protocol.

4.2.1. Duration of Exposure to Study Drug

Total duration of exposure to study drug will be defined as last dosing date minus first dosing date plus 1, regardless of any temporary interruptions in study drug administration, and will be expressed in days. A by-participant listing of study drug administration and drug accountability will be provided by participant ID number (in ascending order) and visit (or timepoint if applicable) (in chronological order).

4.3. Protocol Deviations

Protocol deviations occurring after participants entered the study are documented during routine monitoring. A by-participant listing will be provided for those participants with protocol deviations, including a column specifying whether the protocol deviation is important.

5. BASELINE CHARACTERISTICS

5.1. Demographics and Baseline Characteristics

Participant demographic variables (age, sex at birth, race, and ethnicity) and baseline characteristics (body weight [in kg], body weight-age Z-scores, height/length [in cm], height-age Z-scores, body mass index [BMI; in kg/m²], BMI-age Z-scores, BMI-age percentile, head circumference [in cm]) will be summarized by treatment group (overall and within each cohort/weight group) and overall using descriptive statistics for continuous variables and using number and percentage of participants for categorical variables. The summary of demographic data will be provided for the Safety Analysis Set. Missing values including not permitted will not be included in the denominator when calculating percentages.

A by-participant demographic listing, including the informed consent date, will be provided by participant ID number in ascending order. Note: If information on GA and postmenstrual age (PMA) for participants with GA < 37 weeks and chronological age (CA) < 2 years or length and head circumference for participants < 2 years of age at screening has been collected, this information will be listed. Details on calculating Z-score and percentiles for weight, height/length and BMI are available in Appendix 4.

5.2. Other Baseline Characteristics

Other baseline characteristics include:

- Duration of RSV sign or symptom prior to the first dose of study drug (days)
 - Defined as: First Dosing Date – Onset Date of First/Earliest RSV Sign or Symptom
- Duration from first positive RSV diagnostic test to first dosing date (days)
 - Defined as: First Dosing Date – Date of RSV Diagnosis
- Risk factors for severe RSV disease: (a) None; (b) Yes subdivided into: (i) Aged ≤ 6 months of age; (ii) Aged < 1 year of age and born prematurely (GA < 37 weeks); (iii) Congenital heart disease; (iv) Bronchopulmonary dysplasia; (v) Down syndrome; (vi) Neuromuscular conditions including cerebral palsy
 - Note: Participants may have more than 1 risk factor for severe RSV disease.
- Total number of risk factors for severe RSV disease
- CCI [REDACTED]
- Severity of each targeted RSV symptom at baseline

- Baseline creatinine
- Baseline estimated glomerular filtration rate using Beside Schwartz formula ($eGFR_{\text{Beside Schwartz}}$) (mL/min/1.73 m²)
- Baseline alanine aminotransferase (ALT) (U/L)
- RSV subtype at baseline: (a) RSV-A only; (b) RSV-B only; (c) RSV-A/B Coinfection; (d) Not Determined
- Baseline RSV viral load in UTM Swabs: combined RSV, RSV-A, and RSV-B (as a continuous variable)
- Baseline RSV infectious viral titer (as a continuous variable)

A by-participant listing of other baseline characteristics will be provided by participant ID number in ascending order.

5.3. Medical History

Medical history will be collected at screening for general conditions (ie, conditions not specific to the disease being studied). Medical history will be coded using the current Medical Dictionary for Regulatory Activities (MedDRA) dictionary.

A by-participant listing of medical history will be provided by participant ID number in ascending order.

6. EFFICACY ANALYSES

6.1. Primary Efficacy Endpoint

The FAPS will be used for the primary efficacy endpoint analysis.

6.1.1. Definition of the Primary Efficacy Endpoint

The primary efficacy endpoint is time to alleviation of targeted RSV symptoms by Day 28.

For nonhospitalized participants, alleviation of targeted RSV symptoms is defined as:

CCI

CCI

The date and time of the first day of the 2 daily consecutive assessments will be considered as the date and time of alleviation of targeted RSV symptoms. CCI

. The date and time stamps at which caregivers complete the questionnaire are captured in an electronic diary and the later of the OS assessment time and the DS assessment time will be considered as the assessment time for that day.

CCI

- [REDACTED]
- [REDACTED]
- [REDACTED]
- [REDACTED]
- [REDACTED]
- [REDACTED]
- [REDACTED]

[REDACTED]

[REDACTED]

[REDACTED]

[REDACTED]

6.1.2. Primary Analysis of the Primary Efficacy Endpoint

The primary estimand for the primary efficacy endpoint is outlined in the following table.

Table 6-1. Primary Estimand for Primary Efficacy Endpoint

Attribute	Details
Target population	Study population as defined by protocol eligibility criteria
Treatment condition(s)	ODV and placebo, regardless of treatment discontinuation/modification, RSV-related hospitalization, or RSV-related MAVs
Variable	Time (days) to alleviation of targeted RSV symptoms by Day 28 in the absence of rescue medication and all-cause death
Handling of ICEs	The following scenarios if they occur prior to alleviation of targeted RSV symptoms by Day 28 will be considered: 
• Treatment discontinuation/modification: treatment policy (included as part of the treatment condition(s) attribute)• Use of rescue medication: composite strategy (included as part of the variable attribute). Note: details on the rescue medications are presented in Appendix 4.• All-cause death: composite strategy (included as part of the variable attribute)• RSV-related hospitalization: treatment policy (included as part of the treatment condition(s) attribute)• RSV-related MAVs: treatment policy (included as part of the treatment condition(s) attribute)
Population-level summary	Difference in median variable (as defined in the variable attribute) between ODV and placebo

ICE = intercurrent events; MAV = medically attended visit; ODV = obeldesivir; RSV = respiratory syncytial virus

For participants with targeted RSV symptom alleviation by Day 28 (ie, event), the time to alleviation of targeted RSV symptoms by Day 28 is calculated as the symptom alleviation date/time minus the first dose date/time (expressed as days with 8 decimal places). In the analysis output, 1 decimal place in days will be used for display purposes.

In case, a participant:

- Completes the study without alleviation of targeted RSV symptoms (ie, censored)
- Prematurely discontinues from the study prior to alleviation of targeted RSV symptoms (due to AE, lack of efficacy, investigator's discretion, noncompliance with study drug, protocol violation, participant decision, lost to follow-up) (ie, censored)

The time to alleviation of targeted RSV symptoms will be calculated as the last date and time on which the symptom alleviation is assessed or 23:59:00 on Day 27, whichever occurs first, minus the first dose date and time.

Treatment discontinuation/modification, RSV-related hospitalization, and/or RSV-related MAVs will be ignored (treatment policy).

If a participant takes rescue medication or dies prior to alleviation of targeted RSV symptoms (ie, composite strategy), alleviation of targeted RSV symptoms will not have been achieved. The participant will be censored at the last date and time on which symptom alleviation is assessed prior to the start of rescue medication or death.

CCI

Time to alleviation of targeted RSV symptoms by Day 28 will be summarized using descriptive statistics (n, mean, SD, median, Q1, Q3, minimum and maximum) by censoring status (event or censored) for each treatment group.

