**Table 6. Primary Estimand for Primary Efficacy Endpoint**

Attribute	Details
Target population	Study population as defined by protocol eligibility criteria
Treatment condition(s)	ODV and placebo, regardless of treatment discontinuation/modification, RSV-related hospitalization, or RSV-related MAVs
Variable	Time (days) to alleviation of targeted RSV symptoms by Day 28 in the absence of rescue medication and all-cause death
Handling of ICEs	
The following scenarios if they occur prior to alleviation of targeted RSV symptoms by Day 28 will be considered:
 
 
• Treatment discontinuation/modification: treatment policy (included as part of the treatment condition(s) attribute)
 
• Use of rescue medication: composite strategy (included as part of the variable attribute). Note: details on the applicable rescue medications will be provided in the SAP
 
• All-cause death: composite strategy (included as part of the variable attribute)
 
• RSV-related hospitalization: treatment policy (included as part of the treatment condition(s) attribute)
 
• RSV-related MAVs: treatment policy (included as part of the treatment condition(s) attribute)
 

Population-level summary	Difference in median variable (as defined in the variable attribute) between ODV and placebo

ICE = intercurrent events; MAV = medically attended visit; ODV = obeldesivir; RSV = respiratory syncytial virus; SAP = statistical analysis plan

The estimate of the primary estimand is the difference in median time (days) to alleviation of targeted RSV symptoms by Day 28 in the absence of rescue medication and all-cause death between ODV and placebo as defined by protocol eligibility criteria. This will be estimated regardless of treatment discontinuation/modification, RSV-related hospitalization, or RSV-related MAVs (ie, treatment policy).

The time to alleviation of targeted RSV symptoms by Day 28 is calculated as the symptom alleviation date minus the first dose date. In case, prior to data cutoff a participant:

- Completes the study without alleviation of targeted RSV symptoms
- Prematurely discontinues from the study prior to alleviation of targeted RSV symptoms (due to AE, lack of efficacy, investigator's discretion, noncompliance with study drug, protocol violation, participant decision, lost to follow-up)

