The time to sustained alleviation of targeted RSV symptoms will be calculated as the last date on which the symptom alleviation is assessed minus the first dose date or Day 27, whichever occurs first.

If a participant takes rescue medication or dies prior to alleviation of targeted RSV symptoms (ie, composite strategy) the participant will be censored at the last date on which symptom alleviation is assessed prior to the start of rescue medication or death.

The median time (days) to symptom alleviation along with the associated 95% CI will be estimated by treatment group using the Kaplan-Meier (KM) method. A log-rank test will be used to compare the treatment difference in time to alleviation of targeted RSV symptoms between ODV and placebo. The proportion of participants with alleviation of targeted RSV symptoms using KM estimates will be provided in tables and plots by treatment group.

Furthermore, to support the analysis of the primary efficacy endpoint, a Cox proportional hazards regression model will be used to estimate the hazard ratio and corresponding 95% CI.

Sensitivity analysis associated with the primary endpoint may be performed:

- A nonparametric analysis where the median time (days) to symptom alleviation of targeted RSV symptoms along with the associated 95% CI will be estimated by treatment group using the methodology of Hodges-Lehmann.
- Missing targeted RSV symptom alleviation status will be imputed using multiple imputation assuming missing at random.
- Restricted mean time to alleviation of targeted RSV symptoms will be provided by treatment group.

Subgroup analysis of the primary efficacy endpoint will be performed to investigate the impact of important demographic and other baseline characteristics (eg, cohort, sex, race, risk factors for severe RSV disease). In addition, if important respiratory coinfections are identified at Day 1, a further subgroup analysis of the primary efficacy endpoint to assess the impact of respiratory coinfections will be performed. More details on subgroup analyses will be provided in the SAP.

The number and percentage of participants experiencing an intercurrent event by treatment group will also be provided.

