6.3. Changes From Protocol-Specified Efficacy Analyses

This study was terminated early. Due to the limited number of participants enrolled in the study at the time of study termination, efficacy endpoints will be summarized by treatment group using descriptive statistics only. No inferential analyses will be performed.

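### Rescue medication and death are labelled composite-strategy failures but censored just before they occur, which does not implement a composite strategy; the SAP's descriptive table then does not estimate the stated estimand

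*SAP*

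**What the plan says.** SAP Table 6-1 lists "Use of rescue medication: composite strategy (included as part of the variable attribute") and treats all-cause death the same way. Protocol Table 6 has the same entries, for example "All-cause death: composite strategy (included as part of the variable attribute"). The population-level summary in both is the difference in the median of that variable between ODV and placebo.

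The text below SAP Table 6-1 says that for a child who takes rescue medication or dies first, "alleviation of targeted RSV symptoms will not have been achieved". The next sentence says that the "participant will be censored at the last date and time on which symptom alleviation is assessed prior to the start of rescue medication", and applies the same cut-off to death. Protocol 8.5.1 agrees: "the participant will be censored at the last date on which symptom alleviation is assessed prior to the start of rescue medication or death".

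A child who completes the study unalleviated is handled differently. SAP 6.1.2 censors that child at the last assessment or at 23:59:00 on Day 27, whichever is earlier.

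The planned analyses differ between the documents. Protocol 8.5.1 uses Kaplan-Meier medians, a Cox model and a log-rank test: "A log-rank test will be used to compare the treatment difference in time to alleviation of targeted RSV symptoms between ODV and placebo". The SAP, written after early termination, summarises times with n, mean, SD, median, quartiles and range "by censoring status (event or censored) for each treatment group". SAP 6.3 adds: "No inferential analyses will be performed".

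SAP Table 6-2 repeats the composite label for sustained alleviation and resolution. The table holds labels only; the handling rule reaches those endpoints through the statement in SAP 6.2.2 that analyses similar to 6.1.2 will be performed.

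**The concern.** Under a composite strategy the intercurrent event is part of the outcome. A child who is rescued or dies before alleviation has failed, and stays a non-event to the end of the window. Censoring at the last assessment before the event instead ends that child's contribution while the outcome is still open. That is the usual way to implement a hypothetical strategy under non-informative censoring, and for death it is hard to interpret.

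The consequence depends on the analysis.

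- **Protocol analysis.** The censored child leaves the risk set, and the estimator assumes the same later alleviation rate as in children still followed. Rescue and death stop counting against an arm, although the composite label says they should.
- **SAP table.** The child is not credited with alleviation. But the failure enters the censored row as a short time, alongside completers carried as far as Day 27, and the event row is restricted to children who succeeded. The two rows, separately or together, do not give the difference in medians named in Table 6-1.

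**Working it through.** The documents state no median, rescue rate, death rate or power, so there is no plan figure to reproduce. The size below is illustrative.

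**Assumptions.** Constant hazards; no drug effect on alleviation; no other dropout; follow-up to Day 27 (the SAP's limit). m is the underlying median time to alleviation. r is the share of children in whom rescue or death would come first, ignoring the Day 27 cap.

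**Formulas.**
- Alleviation hazard: λ = ln 2 / m. Total hazard: τ = λ / (1 − r).
- Early-censored Kaplan-Meier median: ln 2 / λ = m, whatever r is.
- Composite: proportion alleviated by t is (1 − r)(1 − exp(−τt)), so the median is −ln(1 − 0.5/(1 − r)) / τ.
- SAP event-row median (alleviated children only): −ln(1 − 0.5(1 − exp(−27τ))) / τ.

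**With m = 6 days, λ = 0.1155 per day:**

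| r | Early-censored KM median | Composite median | SAP event-row median |
|---|---|---|---|
| 0% | 6.00 | 6.00 | 5.63 |
| 2% | 6.00 | 6.05 | 5.54 |
| 4% | 6.00 | 6.11 | 5.44 |
| 5% | 6.00 | 6.14 | 5.40 |
| 20% | 6.00 | 6.79 | 4.66 |

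For r = 20%, τ = 0.1444 and the composite median is −ln(0.375)/0.1444 = 0.981/0.1444 = 6.79.

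**Rescue in 20% of placebo and 4% of ODV (placebo minus ODV):**
- Protocol rule: 6.00 − 6.00 = 0.
- Composite: 6.79 − 6.11 = 0.68 day in favour of ODV.
- SAP event row: 4.66 − 5.44 = −0.78 day, so placebo looks faster because its slower children were more often removed by rescue before they could alleviate.

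**Other medians.** For r from 2% to 30%, the composite median runs from 4.04 to 5.06 days when m = 4, and from 10.09 to 12.65 days when m = 10. The early-censored median stays at 4 and 10.

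**Small-arm example.** Ten children: seven alleviate on days 3, 4, 5, 6, 7, 9 and 12; three are rescued, last assessed on days 1, 2 and 3.
- Early-censored Kaplan-Meier: survival after days 3, 4, 5 and 6 is 7/8, then × 5/6, × 4/5 and × 3/4 = 0.44. The median is 6, and the curve reaches 100% alleviated.
- Composite: the fifth of ten alleviates on day 7. The median is 7, with 70% alleviated.
- SAP table: event-row median 6; censored-row median 2. Carried to Day 27, the censored row would read 27, but the event row would still read 6.

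**The case against.** A reader might infer that the SAP's table treats rescued or deceased children as if they would have alleviated like everyone else. It does not. That describes Kaplan-Meier, log-rank and Cox, which only the protocol plans. The SAP states that these children did not alleviate and puts them in the censored row. The zero difference above is therefore not a planned SAP output.

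A reader might also infer that a real benefit is being hidden in this trial. The documents cannot show that, because no rates are given. Most of the rescue list in SAP Appendix 4 is RSV antivirals and antibodies, the children are nonhospitalized, and protocol 4.3 excludes those expected to need hospitalization within 48 hours or not to survive. Rates may be low, and at 2% to 5% the effect is small. Against that, the list includes chlorpheniramine maleate under a column headed as prohibited ingredients, while protocol 5.3 allows symptomatic medication without restriction and SAP 6.2.2 exempts this drug from the viral-load exclusion. Those passages need to be reconciled, and until then the rescue rate is hard to predict.

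Three further points stand. The trial ended early, was never powered, and no decision rests on the difference in medians. By-participant listings of symptom times, medications and deaths let a reader trace individual cases. And redacted text follows the censoring sentence in SAP 6.1.2, which could add handling rules. None of this reconciles the visible sentence with the composite label: it is complete, and it matches the protocol. Nor does the visible SAP text contain the count of intercurrent events by arm that protocol 8.5.1 promises.

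**Conclusion.** The mismatch is in both documents: a composite label with a censoring rule that does not implement it. Under the protocol's analysis, the composite difference missed is about 0.7 day if alleviation has a 6-day median, is unaffected by the drug, and 20% of placebo and 4% of ODV children are rescued first. A rate of 2% to 5% raises the composite median by about 0.05 to 0.14 day. Under the SAP, the fault is a different one: failures sit as short times in the censored row, the event row is conditional on success, and neither estimates the Table 6-1 difference in medians; the event row can even point the opposite way. All sizes rest on assumed medians and rates. It would go too far to call this a critical flaw in a terminated, descriptive-only trial. It should be fixed, since it governs how the primary efficacy endpoint is read.

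**What to change.** 1. In SAP 6.1.2, replace the censoring sentence with: participants who take rescue medication or die before alleviation are counted as not alleviated and censored at 23:59:00 on Day 27. Use Day 26 for sustained alleviation, the limit already in SAP 6.2.1.1. For resolution, use the matching end-of-window limit; the public text of SAP 6.2.1.2 is incomplete, so check it against the unredacted version.
2. The Day 27 sentence alone changes only the censored row. So also report, by arm, the number alleviated, rescued, dead and otherwise censored, with the median taken over all participants and failures ranked as not alleviated. If that is not wanted, state that the table by censoring status does not estimate the Table 6-1 estimand.
3. Leave the censoring of other study discontinuations unchanged.

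If censoring before the event is really intended, the alternative is to drop the composite label and describe the strategy as hypothetical, with a justification for death.

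The cost is a few lines of SAP text, one derivation and one small table. SAP section 1 says that the plan is finalised before the database is, and that later changes are documented in the CSR. No sample-size figure is affected. The reported overall median will be somewhat longer wherever rescue or death occurred.
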